8.1.2 Intent to Treat (ITT) population

All patients randomized will be included in the ITT population. Patients will be assigned to treatment groups as randomized for analysis purposes.

8.1.3 Safety population

All patients who received at least one dose of study medication will be included in the safety analysis population. Patients will be assigned according to the true treatment received for analysis purposes.

8.2 Data analysis

8.2.1 Analysis of efficacy outcomes

The primary analysis of efficacy will be based on the intent-to-treat principle. The primary endpoint will be compared between the two treatment groups using a chi-square test. Logistic regression models might also be used to compare the primary endpoint between the two treatment groups while accounting for important baseline characteristics. Secondary endpoints will be analyzed similarly. Exploratory analysis (biomarkers) will include logistic regression models with the primary/secondary endpoints as dependent variables and with treatment group, biomarker and treatment group x biomarker interaction as independent variables.

All statistical tests will be two-sided and conducted at the 0.05 significance level, with the exception of the primary analysis that will be conducted at a slightly lower level to account for the interim analysis. Statistical analyses will be done using SAS version 9.4 or higher.

8.2.2 Analysis of safety outcomes

Safety of Fisetin will be evaluated by presenting descriptive statistics for various safety endpoints broken down by group. This will be done for the population of patients who received at least one dose of study medication (safety population).

8.2.3 Interim analysis

A fully independent 5-member Data and Safety Monitoring Board (DSMB) will be established and will review unblinded safety data as detailed in the DSMB charter. An interim analysis is planned after approximately 50% of randomized patients have completed 30 days of follow-up. The DSMB charter will pre-specify the methods of interim efficacy analyses and the rules for early study termination, approved by all board members. The stopping rules for efficacy will be based on the O'Brien-Fleming alpha-spending function or on a similar conservative approach so that the impact on the final alpha level will be negligible. Futility will be assessed by computing conditional power. The DSMB will have the option of recommending early study termination because of overwhelming efficacy, early termination for futility, or continuation of the trial as planned.

The final analysis of the primary endpoint will be conducted at a significance level slightly below

the 0.05 level to account for the interim analysis. However, since this will have a negligible impact on power, the sample size calculation was calculated using a significance level of 0.05.

Appendix A Detailed Study Safety Parameters

1. Demographics and Medical/Surgical History

The following elements of demographics, medical/surgical history will be recorded at the Screening Visit:

- age
- ethnic origin
- sex
- smoking history
- history of diabetes
- history of hypertension
- history of dyslipidemia
- prior cardiac events/heart failure
- prior obstructive pulmonary disease
- prior other respiratory disease

2. Physical Appearance

- 1. weight
- 2. height
- 3. BMI \geq 30 kg/m²

4. Detailed Visit Summary

Screening Visit (Days -2 to 0)

Patients will be pre-screened and inclusion and exclusion criteria will be reviewed prior to being recruited for the study.

- Screening Labs (within 6 months prior to randomization): CBC with diff and comprehensive metabolic panel with assessment of liver and kidney function tests
- Pregnancy test (women of childbearing potential)

Subjects who qualify should be immediately randomized. Randomization and dosing should occur on the same day if possible.

Baseline (Day 0 & Day 1) – IP Administration

- Mail in kit for buccal swab, urine and stool sample prior to first dose of IP administration, if applicable
- SF 36 Health Survey
- Determination of Ordinal Scale Score.
- The 1st IP administration will occur on Day 0.
- The 2nd IP administration will occur on Day 1 (12 -36 hours after the 1st IP administration).
- Day 8 & Day 9 IP Administration Phone call visit with the study team as a reminder for IP administration. This call can occur within a 2 day window (+ or -) of day 8; study drug administration will still occur on day 8 and day 9.
- Determination of Ordinal Scale score.
- Review of adverse events.
- SF-36 Health Survey

- The 3rd IP administration will occur on Day 8.
- The 4th IP administration will occur on Day 9 (12- 36 hours after the 3rd IP administration).

Day $15 - (\pm 2 \text{ days})$

- Determination of Ordinal Scale score.
- Review of adverse events.
- SF-36 Health Survey
- Mail in kit for buccal swab, urine and stool sample, if feasible

Day 30 (-2 to +7 days)

- Determination of Ordinal Scale score.
- Review of adverse events.
- SF-36 Health Survey
- Mail in kit for buccal swab, urine and stool sample, if feasible

Day 60 (±14 days)

- Determination of Ordinal Scale score.
- Review of adverse events.
- SF-36 Health Survey
- Mail in kit for buccal swab, urine and stool sample, if feasible

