3.4 Active Treatment Period

All patients will receive study medication dosing (either Fisetin 100 mg or matching placebo) (PO) ON day 0 and 1 And Day 8 and 9. If a dose is missed, it should not be replaced. Throughout the study, patients will undergo phone visits (at 15, 30, and 60 days) to assess for potential study endpoints and other adverse events (AEs). Patients will be dispensed the entire supply of study medication on Day 0 to use for the duration of the study.

At each phone contact, patients will be:

- 1) questioned in a non-specific manner for the occurrence of AEs and any change in concomitant medications
- 2) 7 point score adapted from the WHO Ordinal Scale for Clinical Improvement of CoV.

Fecal, urine and buccal swab samples for biomarker are optional for the participants. The informed consent form will reflect this option and patients will specifically be asked to consent to this biomarker evaluation.

Please refer to Table 1 and Appendix A for Timetable of Visits and Requirements.

COVFIS-HOME: COVID-19 PILOT STUDY OF FISETIN TO ALLEVIATE DYSFUNCTION AND DECREASE COMPLICATIONS Version 4.0, 18NOV2021

Table 1 Timetable of Visits and Requirements

Visits	1 Screening/Ra ndomization Phone call	2 ^a Randomization/ Baseline Phone call		3 ^b Phone contact		4b Phone contact	5 ^b Phone contact	6 ^b Phone contact
Days		0	1	8 (-/+ 2 days ^d)	9	15 (-/+ 2 days)	30 (-2/+7 days)	60 (-/+ 14 days)
Informed consent	X					· · ·	V	• /
Medical/Surgical history	X							
Review Concomitant Medications	X	X		X		X	X	X
Phone contact	X	X		X		X	X	X
Review Inclusion/Exclusion criteria	X	X						
Urine pregnancy test (only women of childbearing potential)		X		X				
Randomization		X						
SF-36 Health Survey		X		X		X	X	X
Buccal, fecal and urine sample for biomarkers (optional)		X				X	X	Х
Record potential study endpoints (ordinal scale)		X		X		X	X	X
Review Adverse Events		X		X		X	X	X
Study medication dispensing		X						
Study medication dosing		X	X	X	X			

a) Screening Visit 1 and Visit 2 may be performed on the same day; under these circumstances, requirements at both Screening Visit 1 and Visit 2 will be performed once.

b) Phone contact

c) Saliva sample for pharmacogenomics evaluation will be collected using saliva collection kit.

d) Phone contact can occur + or - 2 days; however study drug administration should still occur on days 8 and 9.

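### The Day 8 reminder call may be made on Days 6 to 10 while the doses stay on Days 8 and 9, so the plan lets the reminder follow the doses it is for

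*Combined protocol and SAP*

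**What the plan says.** Appendix A, Detailed Visit Summary, gives the purpose of the Day 8 and Day 9 contact: "Phone call visit with the study team as a reminder for IP administration". It then sets the window: "This call can occur within a 2 day window (+ or -) of day 8; study drug administration will still occur on day 8" and day 9. The dosing lines that follow carry no day window: "The 3rd IP administration will occur on Day 8" and "The 4th IP administration will occur on Day 9 (12- 36 hours after the 3rd IP administration").

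Table 1 in Section 3.4 heads the column with Day 8 and the same two days either side. Its footnote d reads: "Phone contact can occur + or - 2 days; however study drug administration should still occur on days 8 and 9".

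In that column Table 1 marks, among other items, "Review Concomitant Medications", the adverse-event review, the ordinal scale, the SF-36 and "Urine pregnancy test (only women of childbearing potential"). Appendix A's own list for the contact has the ordinal score, the adverse-event review and the SF-36. It has neither the medication review nor the pregnancy test.

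Section 3.4 adds that the whole supply is handed out on Day 0, and says of missed doses: "If a dose is missed, it should not be replaced".

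**The concern.** A reminder is useful only before the event. Here the call can move up to two days later while the doses cannot move at all, so part of the permitted window lies beyond the doses that the call is meant to prompt. A dose forgotten before a late call is lost, because it is not made up.

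The call also carries checks that bear on the second course. Section 4.2.2 and Appendix C require listed drugs to be held from just before the third dose until at least 10 hours after the fourth. Section 5.3 lets the investigator withhold study drug temporarily or reduce it for an adverse event. Both provisions need information that reaches the study team before the second course. All capsules are already in the patient's hands, so no dispensing step on Day 8 would bring that information forward.

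Adherence support and the scheduled safety check before re-exposure are at stake. The efficacy inference is not.

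**Working it through.** The plan states no figure on this point, so there is none to reproduce. The check compares the permitted call days with the fixed dose days.

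**Inputs**
- Nominal contact day 8, window from -2 to +2 days (Table 1 column header, footnote d, Appendix A).
- Third dose on Day 8 and fourth dose on Day 9, with no day window (Appendix A, footnote d).
- Neighbouring phone contacts: Day 0 and Day 15 ± 2 (Table 1). The Day 1 column shows dosing only.

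**Permitted call days**

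8 + {-2, -1, 0, +1, +2} = {6, 7, 8, 9, 10}, which is five days.

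| Call day | Third dose (Day 8) | Fourth dose (Day 9) |
|---|---|---|
| 6 | call first | call first |
| 7 | call first | call first |
| 8 | order not stated | call first |
| 9 | call after dose day | order not stated |
| 10 | call after dose day | call after dose day |

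- After the third dose day: Days 9 and 10, or 2/5 of the permitted days.
- After both dose days: Day 10, or 1/5.
- Certain to precede the third dose: Days 6 and 7, or 2/5.

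**The 12 to 36 hour interval.** If the third dose is taken h hours into Day 8, the latest fourth dose allowed by the interval is at h + 36 hours from the start of Day 8. Day 9 ends at 48 hours, so for h > 12 the interval alone would reach into Day 10. The same line still fixes the fourth dose on Day 9, so a Day 10 call follows both doses as scheduled.

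**Is there another scheduled contact before the second course?** Table 1 shows none after Day 0. The next one is Day 15, and 15 - 2 = Day 13 at the earliest, after both doses.

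**Does any passage require the call to come first?** None does. Section 3.3 puts a pregnancy test before study drug, but as a condition for qualifying, and the rule is not repeated for Day 8. The hold in Section 4.2.2 starts before the third dose, but it binds the patient's other medication and does not set the timing of the call.

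**The case against.** The best defence is that Table 1 and Appendix A agree with each other and address the point openly: the call may move, the doses may not. Read this way, the plus side is a deliberate allowance so that patients not reached by Day 8 still provide adverse-event, SF-36 and ordinal data. Section 3.1 also allows an evaluation at any time for a safety concern. This stands in part. The two places do not disagree, and late data are worth having. It does not explain how a contact described as a reminder serves that purpose after the dose days.

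A reader might infer more than the documents support:

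- *That the call is the only prompt for half the regimen.* Section 6.2 gives patients label instructions naming Days 8 and 9. The call is the only scheduled contact before the second course, not the only prompt, and a Day 9 call may still prompt the fourth dose.
- *That the call is the only safeguard for the Appendix C hold.* Being able to hold a listed drug over both courses is already an eligibility condition (Section 4.2.2). What remains is a listed drug started after Day 0.
- *That late calls blur the tolerability results.* Recorded adverse events carry onset and duration (Section 5.2.1, Appendix B), so they can be placed before or after the second course. The safety analysis is descriptive by group (Section 8.2.2), with no analysis by course.
- *That efficacy is touched.* The versions of the primary endpoint in the Synopsis and Sections 5.1 and 8.1 all refer to Day 30 or the first 30 days. None uses the Day 8 score.

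**Conclusion.** The point holds as a mismatch between a stated purpose and a stated window. Two of the five permitted call days fall after the third dose is due, and one of those falls after both doses. These counts are exact and rest only on the window and the dose days as written. The wrong order is permitted, not required.

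The consequence is limited but real: for a patient called late, there is no scheduled check before the second course for a newly started Appendix C drug or a first-course adverse event. A pre-dose purpose is explicit only for the reminder. For the medication review it follows from the hold. For the second pregnancy test it is an inference from Section 3.3, and footnote d names only the phone contact. The test and the medication review share the window through the column header.

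A reader might turn the 2/5 into patients: if calls were spread evenly over the window, 0.40 × 150 = 60 would be called after the third dose day. The documents say nothing about when calls will actually be made, and an even spread is not a natural assumption for a reminder. The plan allows any number from 0 to 150, so no patient count should be reported.

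The sample size, the endpoints and the primary analysis do not depend on this point. It should be corrected as a matter of conduct and safety oversight.

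**What to change.** Reconcile the contact window with the reminder purpose in three places: the Day 8 column header of Table 1, footnote d, and the Day 8 and Day 9 entry in Appendix A. The contact should be scheduled ahead of the second course. One way is to remove the plus side of the contact window, which leaves Days 6 to 8. The text should then say how a call on Day 8 itself is meant to relate to the third dose.

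In the same edit, state whether the window also covers the urine pregnancy test and the medication review, and bring Appendix A's list for this contact into line with Table 1.

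Keep collecting data when a call is late, and record the actual call date and the actual dose dates, so that each Day 8 record can be placed relative to exposure.

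This changes no dose, dosing day or clinical rule. The cost is a few words in one table, one footnote and one appendix entry. If the plus side is dropped, the contact window is three days instead of five, and some contacts will fall outside it.

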Appendix B Administrative Procedures for the Reporting of Adverse Events

The following administrative procedures for reporting AEs are to be followed during the conduct of this clinical trial.

1 ADVERSE EVENTS DURING THE TRIAL

Each patient will be observed and queried in a non-specific manner by the investigator or study coordinator at each visit for any new or continuing AE since the previous visit. Any AEs prior to the first dose of study medication will be recorded in the medical history and kept in the patients' chart. All SAEs will be recorded in the appropriate eCRF section. In addition to SAEs, the only AEs to be recorded in the eCRF are those that are either related to the gastrointestinal system, that are judged related to the study medication by the investigator or that are laboratory abnormalities judged clinically significant by the investigator. Information collected will include the onset, duration, severity, relationship to study drug, and the management. SAEs are to be reported if they are known to occur within 30 days following the last study visit.

The investigator will review the clinical laboratory test results in a timely fashion when received from the laboratory. Those results qualifying as AEs as defined in this appendix will be recorded on the AE eCRF section and will be handled according to these AE reporting procedures.

The investigator will review concomitant medications being taken by the patient.

Definitions

1.1 Pre-existing condition

A pre-existing condition is one that is present prior to randomization. A worsening of a pre-existing condition after taking the first dose of investigational product should be reported as an AE.

1.2 Adverse Event (AE)

An AE is defined as any unfavorable and unintended sign (including a clinically meaningful abnormal laboratory finding), symptom, or disease temporally associated with the use of an investigational product, whether or not related to the investigational product.

A medical procedure is not considered and should not be reported as an AE. However, the medical condition which led to the procedure should be considered as an AE and be reported as such.

1.3 Related Adverse Event

A related AE is one where, according to the Investigator, there is a reasonable possibility that the event may have been caused by the study drug.

1.4 Serious Adverse Event (SAE)

Serious Adverse Events (SAE) are those that meet any of the following International Council for Harmonisation (ICH) criteria:

- Is fatal or immediately life-threatening (NOTE: the term "Life-Threatening" refers to an event in which the patient was at immediate risk of death at the time of the event; it does not refer to an event which could hypothetically have caused death had it been more severe);
- Results in persistent or significant disability/incapacity;
- Requires or prolongs patient hospitalization;
- Is a congenital anomaly/birth defect in the offspring of the patient;
- Is a cancer;
- Is an overdose (intentional or accidental);
- Is judged to be medically important.

Medically important events may not be immediately life-threatening, result in death or hospitalization, but may jeopardize the patient or may require intervention to prevent one of the outcomes listed in the definition above. Serious adverse events are to be reported if they are known to occur within 30 days following the last study visit.

Medical and scientific judgment should be exercised in deciding whether other AEs meet these criteria and are immediately reportable to the sponsor or its designee.

Version 4.0, 18NOV2021

Hospitalization is defined as a patient admission to a hospital for medical treatment or observation; a visit to the emergency room for an outpatient consultation is not considered a hospitalization. Moreover, the following hospitalizations are not considered SAEs:

- Hospitalizations for diagnostic or elective surgical procedures for a preexisting condition.
- Hospitalization for therapy of the target disease(s) of the study if the protocol explicitly anticipated and defined the symptoms or episodes.
- Hospitalization for study efficacy measurement, as defined in the protocol.

1.5 Life-Threatening Adverse Event

A life-threatening AE is an AE that, in the opinion of the investigator, places the patient at immediate risk of death from the reaction as it occurred.

1.6 Unexpected Adverse Event

An unexpected AE is any AE that is not consistent with findings previously observed.

1.7 Clinical Laboratory Adverse Event

A clinical laboratory abnormality is regarded as an AE if it has been confirmed by at least 1 repeat test and suggests a disease and/or organ toxicity severe enough to require active management.

1.8 Treatment-Emergent Signs and Symptoms (TESS)

A TESS event is any AE that was not present prior to randomization or that worsens in character, intensity or frequency while the patient is in an active treatment period.

1.9 Post-treatment Adverse Event

A post-treatment AE is any AE that occurs after treatment is discontinued.

2 HANDLING OF ADVERSE EVENTS

2.1 Treatment-Emergent Signs and Symptoms

Any condition/diagnosis that meets the definition of a TESS event is captured in the appropriate eCRF AE form and kept in the patient's chart.

2.2 Serious Adverse Events

All SAEs are to be immediately reported. Serious Adverse Events, within 24 hours of the Investigator's first knowledge of the event.

Version 4.0, 18NOV2021

2.3 Intensity

The following criteria are used to assess the intensity of each AE:

- Mild: The patient is aware of the sign or symptom, but finds it easily tolerated.
- Moderate: The patient has enough discomfort to cause interference with or change in usual activities.
- Severe: The patient is incapacitated and unable to work or participate in many or all usual activities.

2.4 Relationship to Study Drug – Physician's Assessment

There are 3 categories for the physician's assessment of the causal relationship between study drug and an AE as follows: not related, possibly and probably.

2.5 Clinical Outcome

The following categories are used to assess the clinical outcome of each AE:

- Death related to the adverse event
- Recovered The patient has fully recovered from the AE without observable residual effects.
- Recovered with sequelae The patient has recovered from the AE with observable residual effects.
- Not Recovered The patient is still being treated for the residual effects of the original AE. This does not include treatment for pre-existing conditions including the indication for the study drug.
- Recovering
- Unknown

3 CAPTURING AVDERSE EVENTS

3.1 Pre-Existing Condition

A pre-existing condition should be captured in the medical history and kept in the patient's chart. If the frequency, intensity, or character of the condition worsens during study treatment, and is either related to the gastrointestinal system, is judged related to the study medication by the investigator or is a laboratory abnormality judged clinically significant by the investigator, it must be documented in the appropriate eCRF AE form.

3.2 Lack of Efficacy of Study Medication

Signs or symptoms defined in the protocol as lack of efficacy or collected as efficacy parameters (endpoints) will be captured as AEs.

3.3 Clinical Laboratory Adverse Event

Version 4.0, 18NOV2021

A clinical laboratory abnormality should be reported as an AE only if it is considered to be clinically significant by the investigator and confirmed by repeat testing.

3.4 Hospitalization or Surgery/Procedure

Any AE reported as study endpoint should not be reported as an SAE. Any condition/diagnosis responsible for surgery/procedure should be reported as an AE if it meets the criteria for an AE. A medical procedure is not considered and should not be reported as an AE. The surgery/procedure itself will be reported as a Clinical Outcome of the underlying event. Events that prolong any hospitalization are reported as SAEs.

3.5 Death

The cause of death should be reported as an AE.

3.6 Other Adverse Events

Study endpoints are to be reported in the eCRF within 24 hours of awareness of the event.

In addition to SAEs and study endpoints, the only AEs to be recorded on the eCRF are those that are either related to the gastrointestinal system, that are judged related to the study medication by the investigator or that are laboratory abnormalities judged clinically significant by the investigator. Information collected will include the onset, duration, severity, relationship to study drug, and the management.

